#### 6.9.4. Vital Signs and Other Physical Findings

Vital signs and physical characteristics include systolic blood pressure (SBP), diastolic blood pressure (DBP), pulse, weight, and BMI. Original-scale data will be analyzed. When these parameters are analyzed as continuous numerical variables, unplanned measurements will be excluded. When these parameters are analyzed as categorical outcomes and/or treatment-emergent abnormalities, planned and unplanned measurements will be included.

The planned analyses described for the laboratory analytes in Section 6.9.3 will be used to analyze the vital signs and physical characteristics, except for the inclusion of a threshold for change in addition to a limit for the definition of treatment-emergent. defines the low and high baseline values as well as the criteria used to define treatment-emergence based on post-baseline values.

**Table DSAD.6.1. Categorical Criteria for Abnormal Treatment-Emergent Blood Pressure and Pulse Measurement, and Categorical Criteria for Weight Changes for Adults**

Parameter	Low mmHg	High mmHg
Systolic BP (mm Hg) (Supine or sitting – forearm at heart level)	$\leq 90$ and decrease from baseline $\geq 20$	$\geq 140$ and increase from baseline $\geq 20$
Diastolic BP (mm Hg) (Supine or sitting – forearm at heart level)	$\leq 50$ and decrease from baseline $\geq 10$	$\geq 90$ and increase from baseline $\geq 10$

Pulse (bpm) (Supine or sitting)	<50 and decrease from baseline $\geq 15$	>100 and increase from baseline $\geq 15$
Weight (kg) (Consistent clothing and timing in relationship to meals and voiding)	(Loss) decrease $\geq 7\%$	(Gain) increase $\geq 7\%$

### **6.9.5. Special Safety Topics, including Adverse Events of Special Interest**

In addition to general safety parameters, safety information on specific topics of special interest will also be presented. Additional special safety topics may be added as warranted.

In general, for topics regarding safety in special groups and circumstances, patient profiles and/or patient listings, where applicable, will be provided when needed to allow medical review of the time course of cases/events, related parameters, patient demographics, study drug treatment and meaningful concomitant medication use. In addition to the safety topics for which provision or review of patient data is specified, these will be provided when summary data are insufficient to permit adequate understanding of the safety topic.

#### **6.9.5.1. Abnormal Hepatic Tests**

Analyses for abnormal hepatic tests will involve 4 laboratory analytes: ALT, AST, total bilirubin, and ALP. In addition to the analyses described in Section 6.9.3, this section describes specific analyses for this topic.

The central laboratory reference ranges (CLRM reference ranges) will be used for these laboratory assessments (ALT, AST, total bilirubin, and ALP).

Analyses for change from baseline to last observation, change from the baseline value to the minimum value during Period 1 and 2, change from the baseline value to the maximum value during Period 1 and 2, and treatment-emergent high or low laboratory results at any time are described in Section 6.9.3.

The patients with the following abnormal elevations in hepatic laboratory tests at any time will be listed for both Period 1 and 2:

- ALT measurement  $\geq 3$  times,  $\geq 5$  times and  $\geq 10$  times the central laboratory ULN.
- AST measurement  $\geq 3$  times,  $\geq 5$  times and  $\geq 10$  times the central laboratory ULN.
- Total bilirubin measurement  $\geq 2$  times the central laboratory ULN.
- ALT or AST measurement  $\geq 3$  times the central laboratory ULN and total bilirubin measurement  $\geq 2$  times the central laboratory ULN
- ALP measurement  $\geq 2$  times the central laboratory ULN.

#### **6.9.5.2. Renal Function Effects**

Effects on renal function will be assessed through analysis of elevated creatinine.

The CTCAE will be applied for laboratory tests related to renal effects (Table DSAD.6.2). This CTCAE grading scheme is consistent with both Version 3.0 and Version 4.03 of the CTCAE guidelines.

Shift tables will show the number and percentage of subjects from baseline to maximum during Period 1 and 2, with baseline depicted by highest grade during the baseline period. A shift table summary displaying the number and percentage of subjects with maximum postbaseline results will be presented by treatment group within the following categories:

- Decreased; postbaseline category < baseline category
- Increased; postbaseline category > baseline category
- Same; postbaseline category = baseline category.

Treatment-emergent lab abnormalities related to elevated creatinine occurring at any time during the Dosing Period will be tabulated using the CTCAE grades shown in Table DSAD.6.2. Planned and unplanned measurements will be included.

Treatment-emergence will be characterized using 5 criteria:

- any increase in postbaseline CTCAE grade from worst baseline grade
- increase to Grade 1 or above at worst postbaseline
- increase to Grade 2 or above at worst postbaseline
- increase to Grade 3 or above at worst postbaseline
- increase to Grade 4 at worst postbaseline.

**Table DSAD.6.2 Common Terminology Criteria for Adverse Events (CTCAE) Related to Renal Effects**

Lab Test	CTCAE Version	Grade	Criteria in SI or CN Units
Elevated creatinine	3.0	0 (normal)	$\leq$ ULN
		1	$>$ ULN and $\leq 1.5 \times$ ULN
		2	$> 1.5 \times$ ULN and $\leq 3 \times$ ULN
		3	$> 3 \times$ ULN and $\leq 6 \times$ ULN
		4	$> 6 \times$ ULN

Abbreviations: CN = conventional (US); CTCAE = Common Terminology Criteria for Adverse Events; SI = Système International; ULN = upper limit of normal.

### 6.9.5.3. Infections

Infections will be defined using the PTs from the MedDRA Infections and Infestations SOC, with additional terms from the Investigations SOC being used in selected instances, as described below.

Treatment-emergent infections will be analyzed according to various groups of infectious events including:

- all infections
  - all PTs in the Infections and Infestations SOC,
- serious infections
  - all PTs in the Infections and Infestations SOC that are SAEs,

- infections that require therapeutic intervention (antibiotics, antivirals, antifungals, and so on)
  - all PTs in the Infections and Infestations SOC for which there is an antimicrobial concomitant medication associated with that event for that subject,
- herpes zoster
  - specific Lilly-defined PTs from the Herpes Viral Infections high-level term (HLT) in the Infections and Infestations SOC, shown in [Appendix 1](#),
- tuberculosis
  - specific Lilly-defined PTs from the Tuberculous Infections HLT and the Investigations SOC, shown in [Appendix 2](#)
- viral hepatitis
  - all PTs from the Hepatitis Viral Infections HLT (HLT code 10057212) in the Infections and Infestations SOC.

For each infection event, the frequency for each PT will be provided, ordered by decreasing frequency in the LY3041658 highest dose group by infection group: all infections, serious infections (overall and on each approach to identifying SAEs), infections that require therapeutic intervention, herpes zoster infections, tuberculosis, and viral hepatitis.

In addition to the incidence of infectious AEs by MedDRA PT as described above, the number and percentage of subjects with treatment-emergent infectious AEs by treatment group will be summarized and listed.

#### Potential Opportunistic Infections:

Potential opportunistic infections (POIs) will be identified according to 2 different approaches.

POIs are identified from TEAEs based on a Lilly-defined list of MedDRA PTs, shown in the [Appendix 3](#). These PTs are a subset of terms from the Infections and Infestations SOC.

For the POIs identified from MedDRA PTs, the number and percentage of subjects overall and for each specific PT will be summarized by treatment group, with specific event terms ordered by decreasing frequency in the LY3041658 highest dose.

#### Association of Infections with Lymphopenia or Neutropenia:

The relationship between the occurrence of lymphopenia and neutropenia with the occurrence of infections will be evaluated based on case reviews. Inferential analyses and/or graphical displays may be conducted if warranted. Infection outcomes considered for this analysis are any infection, any serious infection, infections that require therapeutic intervention (antibiotics, antivirals, antifungals, and so on), tuberculosis, herpes zoster, and viral hepatitis.

#### **6.9.5.4. Allergic Reactions/Hypersensitivities**

A search will be performed using the current MedDRA version 20.0 SMQs to search for relevant events, using the following queries:

- Anaphylactic reaction SMQ (20000021)
- Hypersensitivity SMQ (20000214)

- Angioedema SMQ (20000024)

Events that satisfy the queries will be listed, by temporal order within patient ID, and will include SOC, PT, SMQ event categorization including detail on the scope (narrow or broad), reported AE term, AE onset and end dates, severity, seriousness, outcome, etc.

#### **6.9.5.5. Infusion Site Reactions**

Symptoms of a local infusion site reaction may include erythema, induration, pain, pruritus, and edema. If an infusion site event is reported, the adverse event will be recorded, and additional data will be provided to the sponsor in the eCRF. The number and percentage of patients having any ISR, and each Symptoms (erythema, induration, pain, pruritus, and edema) by maximum severity will be summarized by and treatment for Period 1 using the mITT population. Additionally, summaries of ISR and each Symptoms over by treatment will be provided for each visit.

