2.3. Benefit/Risk Assessment

The efficacy of LY3041658 in HS has not been established. However, LY3041658 decreased neutrophil migration into cantharidin-induced blisters in healthy participants (data on file, Study I7P-MC-DSAA [DSAA]). These findings support the hypothesis that LY3041658 has the

potential for efficacy in HS and other neutrophilic skin diseases. Furthermore, participants may benefit by receiving personal health information from the physical examinations and from other routine safety assessments performed in this study.

At this time, there are no known adverse drug reactions (ADRs) or known risks considered to be associated with LY3041658. No dose-limiting events were observed in the Phase 1 studies DSAA and I7P-MC-DSAB [DSAB].

In the Phase 1 Study DSAA, single doses of up to 700 mg of LY3041658 administered to healthy study participants were generally well tolerated with the exception of a mild, short-lived, infusion-associated reaction in 1 participant in a 700-mg cohort.

In the Phase 1 Study DSAB, participants with psoriasis, HS, or palmoplantar pustulosis received 40 mg to 600 mg doses of LY3041658 every 2 weeks. The most common treatment-emergent adverse events were infections such as cellulitis, sinusitis and respiratory tract infections. Most adverse events were mild to moderate (CTCAE Grade 1 or Grade 2) severity. There was one severe event of elevated gamma-glutamyl transferase (GGT) (CTCAE Grade 3); this event in a single participant assigned to LY3041658 300 mg, and it was not accompanied by symptoms or changes in aspartate aminotransferase (AST) or alanine aminotransferase (ALT) greater than 3 times the upper limit of normal (ULN).

To minimize participant risk in Study DSAD, all participants will be monitored closely after completion of each intravenous (IV) infusion (Section 6.1). In addition, all participants will undergo regular monitoring of routine laboratory safety tests (clinical chemistry, hematology, and urinalysis). Monitoring of safety data will be performed on an ongoing basis, as described in Section 8.2. Interim analyses to review unblinded safety data will also be conducted, as described in Section 9.5 and Appendix 10.1, Section 10.1.5.

In summary, in the context of the cumulative knowledge for LY3041658, the benefit/risk balance for this study is assessed to be favorable.

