8.3.6. Adverse Events of Special Interest

Adverse events of special interest for this study include infusion reactions, systemic hypersensitivity reactions, and infections. If such adverse events are reported, sites will be prompted to collect additional data as described in the following subsections.

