8.3.6.1. Infusion Site Reactions

Symptoms of a local infusion site reaction may include erythema, induration, pain, pruritus, and edema. If an infusion site event is reported, the adverse event will be recorded, and additional data will be provided to the sponsor in the eCRF.

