9.4.5. Safety Analyses

Safety analyses will include adverse events, SAEs, AESIs, C-SSRS, vital signs, ECGs, and laboratory analytes, using the Safety Population data descriptively summarized by treatment group. Categorical safety measures will be summarized with incidence rates. Continuous safety measures will be summarized as mean change by visit. Exposure to study intervention will be calculated for each participant and summarized by treatment group.

Adverse events will be coded according to the *Medical Dictionary for Regulatory Activities* (MedDRA) and summarized by system organ class (SOC), preferred term, severity, and

relationship to the study intervention. A treatment-emergent adverse event (TEAE) is defined as an event that first occurred or worsened in severity after baseline, with baseline defined as all pre-existing conditions recorded at Visit 1 and any adverse events recorded before the first dose of study intervention (that is, during the interval between Visits 1 and 2 and recorded with the time of onset before the first dose of study intervention). The treatment periods will be used as the postbaseline period for the analysis. Safety analyses will be conducted separately for each treatment period. For events that are gender specific, the denominator and computation of the percentage will include only participants from the given gender.

The number and percentage of participants who experienced TEAEs, TEAEs by maximum severity, deaths, SAEs, TEAEs related to study intervention, discontinuations from the treatment due to an adverse event, and AESIs will be summarized. Treatment-emergent adverse events (all, by maximum severity), SAEs including deaths, and adverse events that lead to treatment discontinuation will be summarized and analyzed by MedDRA SOC and preferred term.

Treatment-related TEAEs (TEAEs related to study intervention) are defined as events that are indicated by the investigator on the eCRF to be related to treatment.

Adverse events of special interest will be identified by a standardized MedDRA query (SMQ) or a Lilly-defined MedDRA preferred term listing.

Suicide-related thoughts and behaviors occurring during treatment will be summarized based on responses to the C-SSRS consistent with the C-SSRS Scoring and Data Analysis Guide (Columbia Lighthouse Project WWW).

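### The SAP gives no grouped incidence for hypersensitivity in either period, and none for infusion site reactions in Period 2, although the protocol promises AESI summaries by period on the Safety Population

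*SAP*

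**What the plan says.** Protocol 8.3.6 states: "Adverse events of special interest for this study include infusion reactions, systemic hypersensitivity reactions, and infections". Protocol 9.4.5 plans safety analyses "using the Safety Population data descriptively summarized by treatment group" and adds: "Safety analyses will be conducted separately for each treatment period". In its list of counts and percentages it ends with "discontinuations from the treatment due to an adverse event, and AESIs will be summarized". It also says that AESIs are to be identified by an SMQ or a sponsor-defined list of preferred terms.

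The SAP treats the three AESIs differently:

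- **Infections (6.9.5.3).** Tabulated in defined groups, with counts and percentages by treatment.
- **Hypersensitivity (6.9.5.4).** Three SMQs are run (anaphylactic reaction, hypersensitivity, angioedema). The only output is a listing: "Events that satisfy the queries will be listed, by temporal order within patient ID".
- **Infusion site reactions (6.9.5.5).** Any reaction and five local symptoms are presented "by maximum severity will be summarized by and treatment for Period 1 using the mITT population". The next sentence plans a further summary at each visit by treatment and states no period or population.

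The overview table in SAP 6.9.2 covers adverse events, serious events, deaths and discontinuations, but not AESIs. The infusion AESI also changes name. Protocol 8.3.6 speaks of infusion reactions, whereas Protocol 8.3.6.1 and SAP 6.9.5.5 describe local site reactions only: "Symptoms of a local infusion site reaction may include erythema, induration, pain, pruritus, and edema".

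**The concern.** For two of the three named AESIs the SAP does not specify the summary that the protocol promises. Protocol 9.4 allows the SAP to change analysis methods if it describes and justifies the change. The SAP gives no reason for stopping the infusion site table at Period 1 or for only listing hypersensitivity.

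Two things are at stake. First, Protocol 4.2 gives safety evaluation as one purpose of the open-label period, and former placebo participants receive their first active infusion there. The one table that gives per-participant incidence and maximum severity of infusion site reactions ends before that point. Second, the share of participants in each arm with any hypersensitivity event would have to be counted by hand from a listing, without a prespecified rule for narrow or broad scope or for period.

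**Working it through.** The documents state no infusion count, so there is no figure to reproduce. The check has two parts: how much active exposure lies outside the Period 1 table, and which other outputs cover it.

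**Inputs**
- Arm sizes of 42 active and 21 placebo, 63 in total, with about 45 expected to complete 16 weeks (Protocol 9.2).
- SAP 6.2 still gives 34 and 17, 51 in total.
- Dosing every 2 weeks from Week 0, all participants on active drug from Week 16, last dose at Week 34 (Protocol 4.1 and the Schedule of Activities).
- The Visit 10 (Week 16) infusion is counted in Period 2, because it is the first open-label dose.

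**Infusions per participant**
- Period 1: Weeks 0 to 14, Visits 2 to 9, 8 doses.
- Period 2: Weeks 16 to 34, Visits 10 to 19, 10 doses.

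**Planned active infusions, full dosing**
- Period 1: 42 × 8 = 336.
- Period 2: 63 × 10 = 630.
- Period 2 share: 630 / (336 + 630) = 630 / 966 = 65%.
- With the SAP's numbers: 34 × 8 = 272 and 51 × 10 = 510, so 510 / 782 = 65%.
- Former placebo participants: 21 × 10 = 210 active infusions, all in Period 2.

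**If only 45 continue, each with 10 doses in Period 2**
- Period 2: 45 × 10 = 450.
- Assume the 45 keep the 2:1 ratio, so 30 come from the active arm and 12 active-arm participants drop out.
- If those 12 each received all 8 doses, Period 1 has 336, and 450 / 786 = 57%.
- If those 12 each received 1 dose, Period 1 has 30 × 8 + 12 × 1 = 252, and 450 / 702 = 64%.
- Period 2 drops below half only if the 45 average fewer than 336 / 45 = 7.5 doses (first case) or 252 / 45 = 5.6 doses (second case).

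**What the other SAP outputs cover**

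| Output | Periods | Per-participant grouped AESI incidence? |
|---|---|---|
| Infusion site table by maximum severity (6.9.5.5) | Period 1 | Yes |
| Infusion site summary by visit (6.9.5.5) | No limit stated | No; visit by visit |
| Hypersensitivity listing (6.9.5.4) | No limit stated | No |
| Adverse event tables, also by maximum severity (6.9.2) | By period and overall | No; preferred term within system organ class |
| Listings (6.9) | All safety data | No |

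A participant with two relevant preferred terms appears in two rows, and hypersensitivity terms can fall in several system organ classes. Preferred-term rows therefore cannot be added up to participants with any event. Likewise, visit counts cannot be added up to participants affected during a period.

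**The case against.** The strongest reply is that nothing is lost. The by-visit infusion site summary, read as written, reaches the open-label visits. SAP 6.9.2 counts every treatment-emergent event by period, and by maximum severity at preferred-term level. SAP 6.9 puts these analyses on the Safety Population and says that listings are complete. The protocol's AESI commitment is not withdrawn by silence in the SAP. All of this stands, and it limits the point to missing grouped summaries.

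Four stronger readings are tempting, and the documents do not support them:

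- *Most active infusions are left out of safety reporting.* The 65% applies only to the infusion site maximum-severity table. The hypersensitivity listing has no period limit and omits no infusions.
- *The trial cannot report these AESI rates.* The data exist and individual terms are tabulated. The grouped rate is simply not prespecified.
- *Using mITT changes the population.* SAP 6.3.1 gives mITT and Safety the same members, so the label matters only for someone who received the wrong treatment. The Period 1 limit is the material restriction.
- *Systemic infusion reactions outside hypersensitivity go unrecorded.* All adverse events are collected, and Protocol 8.3.6.2 asks for symptom-level data on systemic hypersensitivity reactions. The Phase 1 "infusion-associated reaction in 1 participant in a 700-mg cohort" was described as mild and short-lived, at a dose above this trial's 600 mg, and nothing shows that such an event would be missed here. What remains is a mismatch of names, which should be reconciled.

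**Conclusion.** The point holds as a misalignment between protocol and SAP. The summary promised in Protocol 9.4.5 is not specified for hypersensitivity in either period, nor for infusion site reactions in Period 2, and AESIs are absent from the overview table. For the infusion site maximum-severity table, the omitted period carries about 65% of planned active infusions. The share is about 57% to 64% if 45 participants continue with full dosing and the active-arm dropouts received between 8 doses and 1 dose each. All active exposure of the former placebo group lies in that period. Event capture is unaffected, and the primary efficacy analysis is not touched. The change is worth making before unblinding because it is cheap and settles the counting rules in advance.

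**What to change.** 1. **SAP 6.9.5.5.** Produce the any-reaction and symptom table by maximum severity for Period 1 and for Period 2, on the Safety Population. Split Period 2 by original arm, so that former placebo and continuing LY3041658 participants are shown separately. State which visits the by-visit summary covers.
2. **SAP 6.9.5.4.** Keep the listing and add the number and percentage of participants per SMQ, narrow and broad, by treatment and period.
3. **SAP 6.9.2.** Add AESIs to the overview table.
4. **Grouping.** SAP 6.9 analyses safety by randomised assignment at Week 0, while SAP 6.3.1 defines the Safety Population by treatment received within each period. State which applies. The Period 2 split in item 1 keeps the original arm visible in either case.
5. **Naming.** Reconcile infusion reactions (Protocol 8.3.6) with infusion site reactions (Protocol 8.3.6.1 and SAP 6.9.5.5). Do not redefine the AESI as any adverse event on an infusion day. That definition has no source in the documents and would bring in coincidental events.

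The cost is a few extra tables from adverse event data already collected, plus minor wording. No new data collection is needed.

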#### **6.9.5.6. Suicidal Ideation and Behavior Risk Monitoring**

Responses to the Columbia Suicide-Severity Rating Scale (C-SSRS) will be summarized by treatment and listed for each patient.

